10.1.5 Expedited Reporting of Serious Adverse Events

All fatal or life-threatening adverse events must be reported to the NMTRC immediately by telephone, fax, or e-mail within 24 hours of knowledge of the event. If full information is not known, additional follow-up by the Investigator will be required.

All other serious adverse events that are related and unexpected (not listed in the relevant appendices) which occur any time after the subject has been consented up to 30 days after the last dose of treatment, and are possibly, probably, or definitely related to the research must be reported to the study chair and appropriate regulatory authorities (local IRB and FDA if required) within 7 days of notification of the event.

The Investigator must report all serious adverse events reported to regulatory authorities in an expedited manner to the local IRB or IEC. All serious adverse events must be followed until resolution or stabilization. Unanticipated problems involving risk to subjects or others, serious adverse events related to participation in the study, and all volunteer deaths related to participation in the study should be promptly reported to the NMTRC.

NMTRC Reporting Contact

Please report all expedited reports to:

[name] and [name]
NMTRC
[contact]
E-Mail: [contact]
E-Mail: [contact]

10.1.6 Grading and Relatedness of Adverse Events

10.1.6.1 Grading of Severity of an Adverse Event

Each adverse event (Grade 2 or higher) will be graded for severity per the National Cancer Institute Common Terminology Criteria for Adverse Events (CTCAE V 4.0), and these criteria must be used in grading the severity of adverse events. The criteria can be found at: <http://ctep.cancer.gov/reporting/ctc.html>.

Grading of Severity of an Adverse Event Not Listed in Published Criteria:

For those adverse events which are not listed as part of the NCI CTCAE V 4.0, the same grading system should be used, where:

- **Mild** corresponds to an event not resulting in disability or incapacity and which resolves without intervention
- **Moderate** corresponds to an event not resulting in disability or incapacity but which requires intervention
- **Severe** corresponds to an event resulting in temporary disability or incapacity and which requires intervention
- **Life-threatening** corresponds to an event in which the subject was at risk of death at the time of the event
- **Fatal** corresponds to an event that results in the death of the subject

10.1.6.2 Relatedness to Study Drug

The Investigator must attempt to determine if an adverse event is in some way related to the use of the study drug and define an attribution category. This relationship should be described as follows:

RELATIONSHIP	ATTRIBUTION	DESCRIPTION
Unrelated to investigational agent/intervention	Unrelated	
The AE is clearly NOT related to the intervention.
 
The event is clearly due to causes distinct from the use of the study drug, such as a documented pre-existing condition, the effect of a concomitant medication, or a new condition which, based on the pathophysiology of the condition, and the pharmacology of the study drug, would be unrelated to the use of the study drug.

	Unlikely	
The AE is doubtfully related to the intervention.
 
Adverse event does not have temporal relationship to intervention, could readily have been produced by the subject's clinical state, could have been due to environmental or other interventions, does not follow known pattern of response to intervention, does not reappear or worsen with reintroduction of intervention.

Related to investigational agent/intervention	Possible	
The AE may be related to the intervention.
 
The event follows a reasonable temporal sequence from administration of the study drug and the event follows a known response pattern to the study drug BUT the event could have been produced by an intercurrent medical condition which, based on the pathophysiology of the condition, and the pharmacology of the study drug, would be unlikely related to the use of the study drug OR the event could be the effect of a concomitant medication.

	Probable	
The AE is likely related to the intervention.
 
The event follows a reasonable temporal sequence from administration of the study drug, the event follows a known response pattern to the study drug AND the event cannot have been reasonably explained by an intercurrent medical condition OR the event cannot be the effect of a concomitant medication.

	Definite	
The AE is clearly related to the intervention.
 
The event follows a reasonable temporal sequence from administration of the study drug, the event follows a known response pattern to the study drug and based on the known pharmacology of the study drug, the event is clearly related to the effect of the study drug. The adverse event improves upon discontinuation of the study drug and reappears upon repeat exposure.

11 SUBJECT WITHDRAWAL AND TRIAL DISCONTINUATION

11.1 Criteria for Subject Off-Therapy

Subjects will be removed from the study therapy for the following reasons:

- Subject completes protocol defined therapy (a minimum of one cycle)
- Progressive neoplastic disease
- Subject or guardian withdraws consent to continue in the trial
- Subject develops an intercurrent illness that precludes further participation, or requires a prohibited concomitant treatment
- The Investigator withdraws the subject in the subject's best interests
- Subject is lost to follow-up (defined as the inability to contact the subject on 3 separate occasions over a period of 2 weeks)
- Administrative reasons (e.g., the subject is transferred to hospice care)
- An adverse event, which in the opinion of the Investigator, precludes further trial participation or fulfills the protocol requirements for withdrawal
- Death

11.2 Criteria for Subject Off-Study

Subjects may be withdrawn from the study completely which includes withdrawal from survival follow-up for the following reasons:

- Completion of all study requirements
- Subject or guardian withdraws consent to continue in the trial (if this occurs, no further study visits or data may be collected)
- Subject is lost to follow-up (defined as the inability to contact the subject on 3 separate occasions over a period of 2 weeks)
- Death

11.3 Trial Discontinuation

The Neuroblastoma and Medulloblastoma Translational Research Consortium (NMTRC) may discontinue the trial as a whole or at an individual investigational site at any time. Reasons for early trial discontinuation may include, but are not limited to, unacceptable toxicity of treatment regimens, a request to discontinue the trial from a regulatory authority, protocol violations at an investigational site, violations of good clinical practice at an investigational site, or poor enrollment. The NMTRC will promptly inform all Investigators in the event of premature study discontinuation and provide all Investigators with instructions regarding the disposition of subjects still on study. Should the study be terminated prematurely, all case report forms and any other study material will be returned to the NMTRC.

12 DATA ANALYSIS

12.1 Data Quality Assurance

Electronic and paper case report forms will be checked for correctness against source document data by the independent study monitor. If any entries into the CRF are incorrect, incomplete or

illegible, the study monitor will ask the Investigator or the study site staff to make appropriate corrections.

12.2 Data Safety Monitoring Board (DSMB)

An independent Data Safety and Monitoring Board (DSMB) will oversee the conduct of the study. The members of this Board will receive database summaries, including adverse event reports, and will convene either in person or via teleconference according to section 3.5. The Board will be responsible for decisions regarding possible termination and/or early reporting of the study.

12.3 Process and Feasibility Analysis

Each of the process measures including the total time to treatment initiation and time to completion of the first cycle of treatment will be described using standard descriptive methods such as means, medians, standard deviations, and 95% confidence intervals. The total time duration to treatment initiation and time to completion of the first cycle of treatment will also be examined using Kaplan-Meier plots since some patients who are considered process failures or who do not complete the full duration to the completion of the first cycle of treatment may contribute censored data. The formal hypothesis testing of the feasibility or success is based upon the 2-stage Mini-Max testing process outlined in Section 8: *Sample Size Justification*. Further quantification of the feasibility success rate will be based upon the percentage of the $n = 16$ patients in each strata who achieve the specified overall time frame limits. This success rate will be supplemented with an exact 95% confidence interval using a Binomial distribution model due to the small sample size involved.

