2.3 Subject Enrollment and Sample Procurement and Data Processing

Eligible subjects will be enrolled onto this study at each site following a registration process that includes receipt of a signed subject consent form and a copy of the required baseline laboratory tests. Subjects will undergo a scheduled surgical resection and/or diagnostic biopsy procedure.

Common sample identifiers will be provided by the NMTRC Lead Study Coordinator to the participating site and will be used by all parties throughout the project to ensure sample, data and report alignment between participating organizations. At the time of tissue resection or biopsy, fresh tumor samples and a blood sample will be committed for this specific research study (referred to as “Primary Samples”), and prepared immediately per Appendix II and section 9.3. Primary Samples will be sent to Ashion Analytics, LLC, which is a CLIA-certified laboratory housed at the Translational Genomics Reserach Institute (TGen). Samples will be reviewed by local pathology to confirm that the sample sent to TGen contains >50% tumor cell viability which is the minimum required for successful analysis. The absence of an adequate tumor specimen from an enrolled subject will make them not eligible to continue on the study. Tumor

samples will also be sent for research purposes (referred to as “Secondary Samples.”) A portion of the tumor tissue biopsy will be shipped overnight to the [name] Pediatric Oncology Translational Research Laboratory on dry ice.

Upon arrival of the tumor specimens at Ashion and the [name] Pediatric Oncology Translational Research Laboratory, the samples will be logged and immediately processed according to details in Section 9.

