5.3.7 Off Therapy/30 Day Follow-Up Visit

Subjects will be followed up at either the study clinic or by telephone within 30 (+7) days after the last dose of treatment. Last dose of treatment is defined as the last day that the subject received a tumor board recommended treatment. The following evaluations will be conducted:

1. Review and recording of concomitant medications;
2. Monitoring of AEs and review of concurrent illnesses;
3. Completion (by study staff) of Case Report Forms.

Any subject with suspected study drug related toxicities at the follow-up visit must be followed until all current drug related adverse events have resolved to baseline or \leq Grade 2 or stabilization of the event. This may require additional clinical assessments and laboratory

tests. The follow-up results will be recorded on the appropriate page of the CRF, as well as in the subject's source documentation.

6 Protocol Drugs

Specific treatment details will consist of a regimen chosen from a guided list of agents implicated in critical molecular signaling pathways and/or from signature-based predictions of drug efficacy summarized from the guided therapy report. All agents are listed in the current pharmacopoeia for human use, but will differ amongst individual subjects. The treatment regimens will be discussed with families and will include review of known side effects per Pharmacopeia Library (Appendix III) (information obtained from package insert and from MicroMedex, LexiComp, Facts and Comparisons, and Natural Medicines Database), serious adverse effects of possible new drug combinations, and any additional clinical monitoring that may be recommended by the tumor board. The family will be given the option to proceed with therapy and if the family decides to proceed with the tumor board's treatment decision they will be asked to sign a treatment specific memo.

Drugs will be prescribed by the enrolling institution per treating hospital protocol and administered per FDA guidelines and tumor board recommendations.

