Assumptions: The feasibility outcome is a binary measure for each of the three clinical strata with a lower success null value of 50% which would require reconsideration of the full process and an upper success value of 75% for the alternative which would be deemed worthy of further consideration for an efficacy trial at the next phase. A binomial distribution was used for the testing process with a combination of Type I error levels (10%) and Power (75%). The basic design overall is a MiniMax approach which minimizes the overall sample size. **The MiniMax design with an interim look will require an overall sample size of n = 16. Each of the three clinical strata will use a two-stage decision rule.**

The Two-Stage Stopping Rule for each of the three strata is as follows:

Stage 1: Stop and accept the null hypothesis if the observed feasibility rate is less than or equal to 5/9. Otherwise, continue to stage 2.

The probability of stopping for futility is 0.746 when H_0 is true and 0.166 when H_a is true.

Stage 2: Stop and accept the null hypothesis if the observed feasibility rate is less than or equal to 10/16. Otherwise, stop and reject the null hypothesis.

As of Amendment 3.0, 100 subjects have been enrolled and all feasibility measures for all strata have been met. To gain additional feasibility with the new Drug Prediction Report and additional safety and efficacy data, additional subjects will be enrolled to meet a revised goal of 200 total evaluable subjects.

The expanded access for 100 patients will enroll following implementation of Amendment 3.0. Their tumor samples will be analyzed using an updated Drug Prediction Report (Appendix III). Overall Response Rate (ORR) and Progression Free Survival (PFS) for this group will be compared to those of the first 100 patients who received treatment based upon the original Drug Predictiton Report and Pharmacopeia Library.

9 Laboratory Evaluations

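### Censoring terminal process failures in the Section 12.3 Kaplan-Meier plots can overstate how many subjects start treatment or complete cycle 1

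*Combined protocol and SAP*

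**What the plan says.** Section 12.3 (Process and Feasibility Analysis) plans standard descriptive statistics for each process measure. It adds that the total time to treatment initiation and the time to completion of cycle 1 will be "examined using Kaplan-Meier plots since some patients who are considered process failures or who do not complete the full duration to the completion" of that cycle may be censored. The sentence ends "completion of the first cycle of treatment may contribute censored data". Censoring of failures is therefore the stated reason for choosing the method. No censoring time is given, and no competing event is mentioned.

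The same section tests feasibility with the two-stage rule of Section 8. It reports a success rate, with an exact binomial 95% interval, as the percentage of the 16 patients per stratum "who achieve the specified overall time frame limits".

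Other sections show that some failures are final:

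- Section 2.3: "The absence of an adequate tumor specimen from an enrolled subject will make them not eligible to continue on the study".
- Section 6: "The family will be given the option to proceed with therapy", so a family may also decline.
- Section 11.1 removes subjects from study therapy for reasons that include "Progressive neoplastic disease", "Subject or guardian withdraws consent to continue in the trial" and death.

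**The concern.** Kaplan-Meier treats a censored subject as someone who would still reach the event at the rate of those who remain at risk. That is reasonable for a subject still in process at data cut-off. It is not reasonable for one whose specimen failed, whose family declined, or who died or left therapy before finishing cycle 1. If these subjects are censored at failure, one minus Kaplan-Meier (1-KM) overstates the proportion that reaches the event. If the censoring comes early, the median time is also too short. When the curve is biased for this reason, it is always in the favourable direction.

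Section 12.3 does not separate terminal failures from subjects who are only late and can still have the event. Two analysts could both follow it and draw different curves from the same data. One report could then show 69% feasibility beside a completion curve that ends near 100%.

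**Working it through.** **The plan's own figures first.** Section 8 stops at stage 1 with 5 or fewer successes of 9. At a 50% success rate the stopping probability is (1+9+36+84+126+126)/512 = 382/512 = 0.746. At 75% it is 0.166. Both match Section 8. The full rule has type I error 0.088 and power 0.753, within the stated 10% and 75%.

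**Inputs for the illustration.** The stratum size is 16 (Section 8). The stage 2 rule is "Stop and accept the null hypothesis if the observed feasibility rate is less than or equal to 10/16", so 11 is the fewest completions that reject the null. The documents give no failure count or failure times, so both are assumed and varied. Every subject's outcome is taken as known, so the true proportion with s completions is s/16. For s = 11 this is 68.75%, with exact 95% interval 41.3% to 89.0%.

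**Formula.** Suppose k of the 16 - s failures are censored before the first completion and the rest are held at risk past the last. The risk set at the first completion is 16 - k. Survival ends at (16 - k - s)/(16 - k), so

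1-KM at the end = s/(16 - k).

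| Completers s | True s/16 | Failures censored early, k | Final 1-KM | Median falls at completion no. |
|---|---|---|---|---|
| 11 | 69% | 0 | 69% | 8 |
| 11 | 69% | 1 | 73% | 8 |
| 11 | 69% | 2 | 79% | 7 |
| 11 | 69% | 3 | 85% | 7 |
| 11 | 69% | 4 | 92% | 6 |
| 11 | 69% | 5 | 100% | 6 |
| 14 | 88% | 0 | 88% | 8 |
| 14 | 88% | 1 | 93% | 8 |
| 14 | 88% | 2 | 100% | 7 |
| 15 | 94% | 0 | 94% | 8 |
| 15 | 94% | 1 | 100% | 8 |

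**Timing.** With s = 11, if all 5 failures are censored at any time before the last completion, only one subject is at risk at that completion and the curve ends at 100%. If all 5 are censored between the 10th and 11th completions, the median stays at the 8th. The end of the curve is therefore more sensitive than the median.

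**Treatment-start curve.** Only subjects who never start matter here, because a subject who fails during cycle 1 has already had this event. One of 16 never starting gives a true 94% against a plotted 94% to 100%. Two of 16 give 88% against 88% to 100%.

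**The alternative method.** Aalen-Johansen with failure as a competing event ends at s/16, with the median at the 8th completion, in every row of the table.

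**Is holding failures at risk in a Kaplan-Meier curve equivalent?** Only if nobody else is censored. Take four subjects: event at time 1, terminal failure at 2, censored at 3, event at 4.

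- Aalen-Johansen: 1/4 + (3/4 × 2/3) × 1 = 0.75.
- Kaplan-Meier with the failure held at risk: 1 - (3/4 × 1/2) = 0.625.

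**The case against.** The strongest reply is about weight. These plots are supplementary. The test and the reported success rate are binomial, and nothing in Section 12.3 says that a percentage or median will be read from the curve. The range of 69% to 100% concerns the tail, where few subjects remain, and it uses the lowest passing count. Section 8 reports that the feasibility measures were met in the first 100 subjects, and Section 1.2 reports 14/14 in an earlier study. All of this stands and limits the size of the point. It does not make the censoring valid.

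Second, it is unclear who would be plotted. Section 2.3 may mean that subjects with inadequate specimens are excluded, and the synopsis separates 200 evaluable subjects from 220 in total. In the earlier study 16 enrolled, 2 were ineligible after biopsy, and 14/14 was reported. If early failures are dropped, only the other routes count. Those routes are not quantified. Progression in cycle 1 would mostly have to be clinical, since Section 5.3.6 sets the first disease assessment at the end of cycle 2 or at 8 weeks. This also stands, but any terminal failure that is plotted and censored still biases the curve.

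Third, the feasibility definition in Section 8 contains no time limit, so a late process failure cannot be identified from the plan. That is true. The proposed remedy does not need the limit, because anyone who can still reach the event stays at risk.

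Fourth, a one-line rule holding failures at risk would be enough once every outcome is resolved. That is correct for a final analysis with no other censoring. It fails when subjects are still in process at data cut-off, as the four-subject example shows.

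**Conclusion.** The concern holds. As written, Section 12.3 allows terminal failures to be censored, and doing so before the last event pushes 1-KM above the true proportion. For one stratum of 16, the overstatement at the end of the curve runs from 0 to 31 percentage points with 11 completers (100 - 69), 0 to 12 with 14 (100 - 88), and 0 to 6 with 15 (100 - 94). The median shifts by at most two, one and zero completions respectively.

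These are illustrations under assumed counts and censoring times, not forecasts. There is no bias if failures are held past the last completion, and little if failures are few. The effect is confined to the descriptive curves and anything read from them. The two-stage decision and the exact binomial interval do not depend on them. It should still be corrected, because these are the planned time displays for the primary objective and they could contradict the report's own success rate.

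**What to change.** In Section 12.3, replace the Kaplan-Meier plots with Aalen-Johansen cumulative incidence curves for treatment start and for cycle-1 completion, and state these rules:

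- Terminal process failure, meaning the subject can no longer reach the event, is a single competing event dated at failure.
- Subjects who are only late stay at risk.
- Only subjects still in process at data cut-off are censored.
- The median, over all enrolled subjects, is the time at which the cumulative incidence curve reaches 50%, with failures counted as never reaching the event. Otherwise it is reported as not reached. If the binomial rate uses a different set of subjects, say so beside the curve.
- Failure reasons are tabulated as counts.

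A Kaplan-Meier curve with failures held at risk to a fixed horizon should not be substituted, because it agrees only when there is no other censoring.

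The cost is two or three sentences, standard software, a failure date and a terminal/late flag for each failure. The analysis is slightly more work, and the curves will look less favourable wherever terminal failures occur.

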ESTIMATED NUMBER OF PATIENTS/GEOGRAPHIC REGIONS	
200 evaluable (220 total) relapsed/refractory pediatric cancer patients. Additional patients may enroll through compassionate access if no other treatment options are available.
 
Patients will enroll at:
 
Arnold Palmer Children's Hospital, FL St. Louis University/Cardinal Glennon Children's Medical Center, MO Helen DeVos Children's Hospital, MI Levine Children's Hospital, NC Connecticut Children's Medical Center, CT Children's Mercy Hospital, Kansas City MO Rady Children's Hospital of San Diego, CA Medical University of South Carolina, SC Monroe Carrell Jr. Children's Hospital at Vanderbilt, TN Kapiolani Medical Center for Women and Children, HI Dell Children's Hospital, TX Texas Children's Hospital, Baylor College of Medicine, TX Primary Children's Hospital, UT Children's Hospital and Clinics of Minnesota, MN Penn State Milton S. Hershey Medical Center and Children's Hospital, Hershey, PA Arkansas Children's Hospital – Little Rock, AR 
International Sites
 American University of Beirut Medical Center, Lebanon La Timone; Marseille, France

LENGTH OF STUDY	Accrual to this study is estimated to be approximately 3-4 years.
STUDY ASSESSMENTS	Refer to Table of Assessments for timing of study procedures.
CRITERIA FOR EVALUATION	
Feasibility Measures: Primary objective: The definition of feasibility for this study will include: “Enrollment onto study, genomic profile, analysis and report generation completed, tumor board held with treatment decision, treatment review completed, start of treatment, and completion of 1 cycle of therapy.”
 
Efficacy Measures: Secondary objectives Response: To determine the overall response rate (ORR) by the presence of radiologically assessable disease by cross-sectional CT or MRI imaging and/or by MIBG or PET scans.
 
 ◆ Duration of response, defined as the period of time from when measurement criteria are met for complete response (CR) or partial response (PR), whichever is first recorded, until the first date that recurrent or progressive disease (PD) is objectively documented (taking as reference for PD the smallest measurements recorded since the treatment started) ◆ The assessment of response will include the initial measurable

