3.6 Treatment during waiting period

Subjects will be allowed to receive one cycle of standard of care or treating physician chosen therapy after their biopsy and before starting tumor board defined therapy in order to prevent progression during this waiting period. Subjects that opt to have this cycle of therapy will need to have recovered from hematological effects (to baseline) and have repeat scans of their primary tumor sites and any sites being followed for study efficacy before starting tumor board defined therapy.

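### Kaplan-Meier plots in Section 12.3 may censor subjects who can no longer start or complete cycle 1; if censored when lost, these descriptive curves run too high, mainly at the right-hand end (minor)

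*Combined protocol and SAP*

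**What the plan says.** Section 12.3 (Process and Feasibility Analysis) first describes the process times by means, medians, standard deviations and confidence intervals. It then says that time to treatment initiation and time to completion of cycle 1 "will also be examined using Kaplan-Meier plots". The reason given is that some subjects classed as "process failures or who do not complete the full duration to the completion of the first cycle of treatment may contribute censored data". The section does not say which failures would be censored, or at what time, and it names no competing-event method.

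The formal decision lies elsewhere. Section 8 sets a two-stage binomial rule per stratum, whose second stage reads "Stop and accept the null hypothesis if the observed feasibility rate is less than or equal to 10/16". Section 12.3 adds a success percentage in the 16 patients per stratum with an exact 95% confidence interval. The feasibility definition is a chain of steps that ends with "treatment review completed, start of treatment, and completion of 1 cycle of therapy", so a subject who drops out anywhere along it is a failure.

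Several exits are permanent:
- Section 2.3 on tissue: "The absence of an adequate tumor specimen from an enrolled subject will make them not eligible to continue on the study".
- Section 6 on refusal: "The family will be given the option to proceed with therapy".
- Section 11.1 lists reasons for removal from study therapy, among them progression, withdrawal of consent, an adverse event and death.

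Section 3.6 allows one bridging cycle after biopsy "in order to prevent progression during this waiting period".

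**The concern.** Kaplan-Meier censoring treats a subject as someone who might still have the event later, with the same chance as those still under observation. That suits a child who is waiting for the tumor board at data cutoff. It does not suit a child whose specimen was inadequate, whose family declined, or who died before dosing. Nor does it suit, for cycle 1 completion, a child who stopped therapy for good during that cycle. Removing these children from the risk set when they are lost shares their probability among those who remain, and the curve climbs above the proportion that truly started or completed.

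The stake is descriptive, but it concerns the process that the trial was set up to study. A curve rising to 100% could stand in the same report as a success rate well below that. The success percentage in Section 12.3 is tied to 16 patients per stratum, whereas the plots are not. For the second 100 subjects, enrolled in part "To gain additional feasibility with the new Drug Prediction Report" (Section 8), the process summaries and these plots are the Section 12.3 outputs not limited to those 16.

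**Working it through.** **1. The plan's own figures (Section 8).** The probability of stopping at stage 1 is the sum over x = 0 to 5 of C(9,x) p^x (1−p)^(9−x).
- p = 0.50: (1 + 9 + 36 + 84 + 126 + 126)/512 = 382/512 = 0.746, as stated.
- p = 0.75: 0.166, as stated.
- The full rule (5/9, then 10/16) has exact type I error 0.088 and power 0.753, within the stated 10% and 75%.

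The rule counts failures as failures and uses no Kaplan-Meier estimate.

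**2. Direction of the error.** At each event time Kaplan-Meier multiplies by 1 − d/r, where d is the number of events and r the number at risk. If permanent failures are removed when lost, r is smaller than if they are kept, so each step is larger. The plotted proportion, 1 − KM, can therefore only equal or exceed the true proportion (events so far divided by all enrolled).

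**3. One stratum at the plan's 75% target.** Inputs: n = 16 and the 75% alternative (Section 8). Starts are evenly spaced over days 7–20, the range in the earlier neuroblastoma feasibility trial (Section 1.2). Assumed: 12 start and 4 are lost on day 10.
- By day 10, 3 have started: (15/16)(14/15)(13/14) = 13/16.
- The 4 losses leave 9 at risk. Three more start by day 14: (8/9)(7/8)(6/7) = 6/9.
- Day 14: 1 − (13/16)(6/9) = 45.8%. True: 6/16 = 37.5%.
- Day 20: the last subject at risk starts, so the curve reads 100%. True: 12/16 = 75%.
- If the 4 losses are spread over days 6–19, day 14 reads 41.8% and day 20 reads 100%.
- If they are held at risk to day 21, the curve reads 37.5% and 75%, with no bias.

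**4. Cycle 1 completion at the failure boundary, as an extreme.** 10 of 16 complete: 62.5% (exact 95% CI 35.4–84.8). Assumed: completions evenly spaced over days 35–48 (7–20 days plus a 28-day cycle) and 6 losses evenly spaced over days 1–47.
- Day 42: five completions with 12, 11, 9, 8 and 7 at risk. 1 − (11/12)(10/11)(8/9)(7/8)(6/7) = 1 − (10/12)(6/9) = 44.4%. True: 5/16 = 31.3%.
- Day 48: 100%. True: 62.5%.
- With random timing instead (completions uniform on days 35–48, losses uniform on days 0–48, 5,000 runs), the curve ends at 98.5% on average and at 100% in 86.5% of runs.

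**5. Whole trial.** N = 220 total against 200 evaluable (Synopsis). Assumed: k subjects lost before dosing, evenly over days 1–19, and starts evenly over days 7–20.

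| k | Kaplan-Meier end | True end, (220−k)/220 |
|---|---|---|
| 5 | 100% | 97.7% |
| 10 | 100% | 95.5% |
| 20 | 100% | 90.9% |

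- Day 14, k = 20: 51.8% against 108/220 = 49.1%.
- Median time to treatment: 13.8 against 14.1 days for k = 20; 13.56 against 13.62 days for k = 5.
- All losses censored at day 21: the Kaplan-Meier end equals the true end for each k.

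**6. Cycle 1 completion, whole trial.** With 20 lost before dosing and an assumed 10, 20 or 40 of the other 200 stopping in cycle 1, the true rate is (200−m)/220 = 86.4%, 81.8% or 72.7%. The curve ends at 100% whenever the last completion follows the last loss.

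**The case against.** The strongest reply is that no decision rests on these plots. Section 12.3 puts formal testing in the two-stage rule and quantifies success by an exact binomial rate. The plots are an addition. This stands, and it is why the point is minor. A reader might infer that the feasibility conclusion itself is inflated, but the documents do not support that, because the composite counts every lost subject as a failure.

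Second, the wording is permissive and gives no censoring time. If failures were held at risk past the last event there would be no bias. That also stands, so the claim has to be conditional. It is not a defence of the text, since a correct curve then depends on a choice that the plan does not record.

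Third, the numbers are illustrative. The 7–20 days come from an earlier gene-chip trial, were measured from biopsy, and had a 21-day start limit that is absent here. The present trial uses sequencing and allows a bridging cycle. Reading the gap of 220 − 200 = 20 as losses before dosing is a guess. The earlier rates given are 14/14 (Section 1.2) and 5/5 (Section 8). Section 8 also says that feasibility had been met in all strata by Amendment 3.0, so the 10/16 case is not what happened in the first cohort. All of this limits the size of the error but not its direction.

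Fourth, a reader might infer that any child who progresses before dosing is lost. No section says so. Section 4.1 admits relapsed and progressive disease. Sections 3.6 and 5.2 require repeat scans and blood-count recovery after bridging, but do not bar a child who has progressed. Section 11.1 concerns removal from study therapy. Section 3.6 shows concern about progression during the wait, not that the wait causes losses. Counting every progression as a failure would push the curve too low.

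**Conclusion.** The point holds in a limited form. If subjects who can permanently no longer start, or no longer complete cycle 1, are censored when lost, the two descriptive curves overstate the proportion started or completed. The direction is certain under that condition. The size depends on loss counts and dates that the documents do not give.

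For losses of 5 to 20 in 220, the right-hand end is too high by 2.3 to 9.1 percentage points (100 − 97.7 and 100 − 90.9), while the median moves by about 0.1 to 0.3 day. In one stratum of 16 with a quarter lost, the end is too high by 25 points and day 14 by 4.3 to 8.3 points. The bias is nil if failures remain at risk past the last event. The two-stage test and the exact binomial rate are untouched. Severity: minor.

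**What to change.** In Section 12.3, replace the Kaplan-Meier plots with cumulative incidence curves in all enrolled subjects, timed from enrollment (Section 5.2 lets the tissue predate enrollment by up to 12 weeks).

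- **Time to treatment:** count as a competing event only a permanent failure to start tumor-board therapy. This means death, inadequate tissue, withdrawal or refusal, or a documented decision not to treat, including one due to progression or deterioration. Progression before dosing in a child who later starts is not a competing event.
- **Time to cycle 1 completion:** add permanent discontinuation during cycle 1.
- **Censoring:** only subjects still waiting, or still in cycle 1, at data cutoff.

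A simpler alternative is to keep permanent failures in the risk set to the end of the observation window. This gives the same curve once no subject is still in process.

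The cost is a change of wording and a standard estimator. One case report form field for the reason treatment was never started may be needed, because Section 11.1 lists reasons only for leaving therapy. The curves will look slightly less favourable. Sample size, visits and the decision rule do not change.
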